1 INTRODUCTION

1.1 Study Objectives

Primary Study Objective	To evaluate the effects of dapagliflozin vs. placebo on heart failure related health status using the Kansas City Cardiomyopathy Questionnaire (KCCQ) clinical summary score at 12 weeks.
Secondary Study Objectives	
1. To evaluate the effect of dapagliflozin vs. placebo on heart failure related health status using the Kansas City Cardiomyopathy Questionnaire (KCCQ) overall summary score at 12 weeks2. To evaluate the effect of dapagliflozin vs. placebo on NTproBNP at 6 and 12 weeks3. To evaluate the effect of dapagliflozin vs. placebo on BNP at 6 and 12 weeks4. To evaluate the effect of dapagliflozin vs. placebo on 6-minute walk test at 12 weeks5. To evaluate the effect of dapagliflozin vs. placebo on HbA1c over the treatment period (evaluated separately in patients with and without type 2 diabetes)6. To evaluate the effect of dapagliflozin vs. placebo on proportion of patients with a \geq 5pts increase in KCCQ clinical summary score and KCCQ overall summary score at 12 weeks7. To evaluate the effect of dapagliflozin vs. placebo on proportion of patients with a \geq 20% decrease in NTproBNP at 6 and 12 weeks8. To evaluate the effect of dapagliflozin vs. placebo on proportion of patients with a \geq 5pts increase in KCCQ and a \geq 20% decrease in NTproBNP at 6 and 12 weeks9. To evaluate the effect of dapagliflozin vs. placebo on weight at 6 and 12 weeks10. To evaluate the effect of dapagliflozin vs. placebo on systolic blood pressure at 6 and 12 weeks
Exploratory objectives	
1. To evaluate the effect of dapagliflozin vs. placebo on composite hierarchical-rank clinical score.2. To evaluate the effect of dapagliflozin vs. placebo on heart failure hospitalizations3. To evaluate the effect of dapagliflozin vs. placebo on urgent heart failure visits4. To evaluate the effect of dapagliflozin vs. placebo on heart failure hospitalizations and urgent heart failure visits

	
 5. To evaluate the effect of dapagliflozin vs. placebo on the proportion of patients that progress to diabetes during the treatment period (within the subgroup of patients without diabetes at baseline only) 6. To evaluate the effect of dapagliflozin vs. placebo on weekly loop diuretic dose (furosemide equivalent) 7. To evaluate the effect of dapagliflozin vs. placebo on NYHA Class at 6 and 12 weeks. 8. To evaluate the effect of dapagliflozin vs. placebo on left atrial volume index and other measures of left ventricular diastolic function (among Echocardiography sub study participants only)
--	---

1.2 Study Design

Design Configuration and Subject Population	Randomized, double-blind, placebo-controlled trial. The control group will receive placebo administered orally once daily for 12 weeks plus standard of care. The treatment group will receive dapagliflozin 10 mg administered orally once daily for 12 weeks plus standard of care. A follow-up visit at week 13 will be performed to evaluate markers of renal function.
Treatment Groups	Dapagliflozin 10 mg or matching placebo administered orally once daily for 12 weeks, in addition to standard of care for chronic heart failure with preserved systolic function.
Inclusion criteria	
 1. Age > 18 and < 120 at the screening visit 2. Symptoms of dyspnea (NYHA class II-IV) without evidence of a non-cardiac or ischemic explanation for dyspnea 3. Ejection fraction (EF) $\geq 45\%$ as determined on imaging study within 24 months of enrolment with no change in clinical status suggesting potential for deterioration in systolic function 4. Elevated NT-proBNP (≥ 225 pg/ml) or BNP (≥ 75 pg/ml) \dagger 5. Stable medical therapy for heart failure for 15 days as defined by: 
 i. No addition or removal of ACE, angiotensin receptor blockers (ARBs), valsartan/sacubitril, beta-blockers, calcium channel blockers (CCBs) or aldosterone antagonists ii. No substantial change in dosage (100% or greater increase or decrease from baseline dose) of ACE, ARBs, beta-blockers, CCBs or aldosterone antagonists 6. On a diuretic ≥ 15 days prior to screening visit and a stable diuretic therapy for 7 days 7. At least one of the following: 
 i. Hospitalization for decompensated HF in the last 12 months ii. Acute treatment for HF with intravenous loop diuretic or hemofiltration in the last 12 months

	
 iii. Mean pulmonary capillary wedge pressure ≥ 15 mmHg or LV end diastolic pressure (LVEDP) ≥ 15 mmHg documented during catheterization at rest, or pulmonary capillary wedge pressure or LVEDP ≥ 25 mmHg documented during catheterization with exercise. iv. Structural heart disease evidenced by at least one of the following echo findings (any local measurement made within the 24 months prior to screening visit): 
 1) left atrial (LA) enlargement defined by at least one of the following: LA width ≥ 3.8 cm or LA length ≥ 5.0 cm or LA area ≥ 20 cm² or LA volume ≥ 55 mL or LA volume index ≥ 29 mL/m² 2) OR left ventricular hypertrophy (LVH) defined by septal thickness or posterior wall thickness ≥ 1.1 cm.
Exclusion criteria	
 1. Decompensated heart failure (hospitalization for heart failure within 7 days prior to screening) 2. History of type 1 diabetes 3. History of diabetic ketoacidosis 4. Estimated glomerular filtration rate (eGFR) < 20 at the screening visit by modified MDRD equation GFR (mL/min/1.73 m²) = 175 x (Scr) $-1.154 \times (\text{Age}) - 0.203 \times (0.742 \text{ if female}) \times (1.210 \text{ if African American})$ 5. Admission for an acute coronary syndrome (ST-elevation MI, non-ST-elevation MI, or unstable angina), percutaneous coronary intervention, or cardiac surgery within 30 days prior to the screening visit. 6. Admission for cardiac resynchronization therapy (CRT) within 90 days prior to the screening visit. 7. Planned cardiovascular revascularization (percutaneous intervention or surgical) or major cardiac surgery (coronary artery bypass grafting, valve replacement, ventricular assist device, cardiac transplantation, or any other surgery requiring thoracotomy, or transcatheter aortic valve replacement) or CRT within the 90 days after the screening visit. 8. Participation in any interventional clinical trial (with an investigational drug or device) that is not an observational registry within 15 days of the screening visit. 9. History of hypersensitivity to dapagliflozin 10. For women of child-bearing potential: Current or planned pregnancy or currently lactating. 
Women of childbearing potential are defined as any female who has experienced menarche and who is NOT permanently sterile or postmenopausal. Post menopausal is defined as 12 consecutive months

	
with no menses without an alternative medical cause. Women of child-bearing potential, who are sexually active, must agree to use a medically-accepted method of birth control for the duration of the study. Acceptable birth control methods include: (1) surgical sterilization (such as a hysterectomy or bilateral tubal ligation), (2) progesterone hormonal contraceptives (birth control pills or implants), (3) barrier methods (such as a condom or diaphragm) used with a spermicide, or (4) an intrauterine device (IUD). Women of child-bearing potential will have a urine pregnancy test at every clinic visit and it must be negative to continue study participation.
 
11. Life expectancy <1 year at the screening visit
 
12. Patients who are volume depleted based upon physical examination at the time of the screening or randomization visit
 
13. BNP <75 pg/mL and NTproBNP<225 pg/mL at the screening visit
 
14. Patients currently being treated with any SGLT-2 inhibitor (dapagliflozin, canagliflozin, dapagliflozin, ertugliflozin) or having received treatment with any SGLT-2 inhibitor within the 12 weeks prior to the screening visit.
 
15. Average supine systolic BP <100 mmHg at the screening or randomization visit
 
16. Current history of bladder cancer
 
17. Donation of blood or bone marrow 12 weeks prior to the screening visit and no planned donations during the study period
 
18. Heart failure due to restrictive/infiltrative cardiomyopathy, active myocarditis, constrictive pericarditis, severe stenotic valve disease, and HOCM (hypertrophic obstructive cardiomyopathy).
 
19. Heart failure due to severe aortic or mitral regurgitation
 
20. Severe COPD thought to be a primary contributor to dyspnea
 
21. Isolated right heart failure due to pulmonary disease
 
22. Active and significant ischemia thought to be a primary contributor to dyspnea
 
23. Documentation of previous EF < 45%, under stable conditions, within the past 36 months
 
24. Complex congenital heart disease
 
25. Uncontrolled hypertension, defined as systolic blood pressure ≥200 mmHg during the screening visit (average value of three blood pressure measurements obtained in supine position)

--	--

	
26. Any other condition that in the judgment of the investigator would jeopardize the patient's participation in the study or that may interfere with the interpretation of study data or if the patient is considered unlikely to comply with study procedures, restrictions and requirements
 
27. Bariatric surgery within the past 6 months or planned bariatric surgery within the study time course.
 
28. CardioMems device implantation within previous 4 weeks or planned CardioMems implantation during study period
 
29. For echo substudy only: patients with ventricular paced rhythm or left bundle branch block on the most recent clinically available 12-lead electrocardiogram.
 
30. For echo substudy only: permanent atrial fibrillation
 
† For patients with permanent atrial fibrillation inclusion thresholds will be BNP \geq 100 pg/mL or NTproBNP \geq 375 pg/mL
 
‡ For patients with permanent atrial fibrillation exclusion thresholds will be BNP $<$ 100 pg/mL and NTproBNP $<$ 375 pg/mL

--	--

1.3 Sample Size and Power

Planned Sample Size	Approximately 160 patients will be enrolled in each arm.
Power Statement	For the primary endpoint a sample size of 145 for each group will achieve 82% power with $\alpha=0.05$ to detect a 4.7 difference in mean KCCQ CS between dapagliflozin group and placebo group at 12 weeks. The assumptions for this calculation was derived from DEFINE-HF trial where the adjusted mean difference between dapagliflozin group and placebo group is 4.7 and the standard deviation is 13.7. Assuming a 10% loss to follow up, we arrive at a sample size of ~320 patients.

2 GENERAL CONSIDERATIONS FOR DATA ANALYSES

2.1 Analysis Data Sets

Efficacy and safety analyses will be performed on data from the following analysis sets:

- Enrolled patients set (EPS) will consist of all patients who signed the informed consent. This data set will be used to summarize the patient disposition data.
- Modified intention to treat set (modified ITTS) is defined as all patients who have been randomized to study treatment, have received at least one dose of study medication, and have sufficient evaluable data for endpoint ascertainment during follow up. For clarity, patients with no evaluable data for a particular outcome during follow up will be excluded from the analyses of these respective endpoints. Subjects will be analysed according to the randomization group. The modified ITTS data set will be used for the primary, secondary, and selected exploratory (, NYHA class, loop diuretic dose, progress to DM, left atrial volume index and other measures of left ventricular diastolic function) efficacy endpoints. Progress to DM will be assessed among participants in the modified ITTS who had no diabetes at baseline. Left atrial volume index and other measures of left ventricular diastolic function will be assessed among participants who are in the modified ITTS dataset and also in the Echocardiography sub study.
- On-treatment set (OTS) includes all subjects in the modified ITTS. Primary and secondary endpoint measurements will be excluded for the follow-up time point(s) when subjects were temporarily or permanently off the study drug at the time the corresponding measurements were obtained. The OTS data set will be used for a sensitivity analyses for the primary, secondary, and selected exploratory (composite hierarchical rank clinical score, NYHA class, loop diuretic dose) efficacy endpoints.
- The per protocol set (PPS) includes all subjects in the modified ITTS who did not have any major protocol deviations. Major protocol deviations, which are detailed in section 2.2, will be determined prior to unblinding of treatment groups. Subjects will be summarized according to actual treatment received regardless of the allocated treatment. This will be used for a sensitivity analysis for the primary efficacy endpoints only.
- The safety analysis set (SAFS) includes all patients who received at least 1 dose of study medication. Throughout the safety results sections, erroneously treated patients (eg, those randomized to dapagliflozin but actually given placebo) will be accounted for in the actual treatment group. If a patient received study drug from the wrong kit for only a part of the treatment duration and then switched to another, the associated actual treatment group for that patient will be the treatment group the patient had the longest exposure to. The main safety analyses will be restricted to adverse events that occurred between randomization and the 12-week visit. Adverse events that occurred between 12 weeks and 13 weeks (after discontinuation of study treatment) will be collected, and presented in a

separate, supplemental analysis. The safety analysis set will be used to summarize safety data and patient demography and their baseline characteristics, and to analyze selected exploratory endpoints (composite hierarchical-rank clinical score, heart failure hospitalizations, urgent heart failure visits, and a composite of heart failure hospitalizations or urgent heart failure visits). If there is a difference between the SAFS and modified ITTS, baseline and demography data will also be presented for the IITS.

2.2 Protocol Deviations and Major Eligibility Violations

Important Protocol Deviations (IPDs) are defined as those important deviations from the protocol that are likely to have an impact on the efficacy and/or safety of study treatments, or integrity of study data.

Protocol deviations will be reviewed in a blinded fashion by the study team prior to database lock. All decisions to exclude patients and/or data from the modified ITTS or PPS will be made prior to the unblinding of the study and agreed by the study team.

Error! Reference source not found.10.2 specifies the criteria for IPDs.

2.3 Strata, Covariates, and pre-specified subgroup analyses

All efficacy and safety endpoints will be analyzed in the entire cohort, and then within the subgroups of patients with and without diabetes. Analyses for the primary and secondary endpoints will be adjusted for the corresponding baseline measurements as well as sex, eGFR, diabetes (DM), permanent AFib, and LVEF. Restricted cubic splines will be used for continuous variables to accommodate non-linear effects, as appropriate.

A sensitivity analysis will repeat the primary analysis but will also include site as a random effect to account for potential clustering by enrolling centers. Another sensitivity analysis for the primary endpoint will be performed using the imputed KCCQ values as described in section 2.6.

Additionally, the following pre-specified subgroup analyses will be performed for the primary endpoints (stratified by the baseline variables below):

- Baseline NTproBNP (< median, \geq median)
- Baseline LVEF (\leq 60%, $>$ 60%)
- Atrial fibrillation type (No AFib, permanent/persistent AFib, paroxysmal AFib)
- Baseline KCCQ overall summary score (<median, \geq median)
- Baseline eGFR ($<$ 60, \geq 60 mL/min/1.73 m²)
- Age ($<$ 70, \geq 70)
- Sex (male, female)
- Race (white, non white)
- BMI(<median, \geq median)

- Furosemide equivalent mean daily dose: ≤ 40 mg, >40 mg
- NYHA Class (II, III or IV)

Subgroup analyses will be carried out by augmenting the primary analysis model with terms for subgroup and a subgroup-by-treatment interaction. Adjusted point estimates and 95% confidence intervals will be calculated for the effect of dapagliflozin compared with placebo within each subgroup. An interaction p-value will be provided.

Due to the large number of study sites and the expected low number of patients per site, site effects will not be explored, although study site will be included as a random effect in efficacy sensitivity analyses to account for within-site correlations, as specified above.

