We plan to repeat the analysis within the subgroups of patients with and without diabetes. Assuming 60% of the patients do not have type 2 diabetes, the non-diabetes stratum is estimated to have ~174 patients (~87 each arm), which will achieve 80% power with $\alpha=0.05$ to detect a 5.9 difference in mean KCCQ CS between dapagliflozin and placebo at 12 weeks; assuming 10% loss to follow up, we arrive at a sample size of ~192 patients within the no diabetes subgroup (~60% of the total sample). This will provide a large enough subgroup of patients with no diabetes to provide preliminary data on the effects of dapagliflozin vs. placebo in this important subgroup – in which the effects of SGLT2 inhibitors have not been well described. For the diabetes subgroup, a sample size of 58 for each arm will achieve 80% power with $\alpha=0.05$ to detect a 7.2 difference in mean KCCQ CS between dapagliflozin and placebo at 12 weeks.; assuming 10% loss to follow up, we arrive at a sample size of ~128 patients within the diabetes subgroup (40% of the total sample). The above calculations demonstrate that the current overall study sample size is sufficient to examine the effects of dapagliflozin vs. placebo on the primary endpoint; and will provide sufficient numbers of patients within the key subgroups (diabetes, no diabetes) to examine whether important interactions exist in the effects of dapagliflozin vs. placebo by diabetes status.

Of note, participation of patients with permanent atrial fibrillation is allowed, but may be capped at no more than 33% (105 patients) of the entire cohort.

Due to the large number of study sites and the expected low number of patients per site it will not be appropriate to explore site effects.

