2.5 Multiple Testing

The primary endpoint will be tested at the 2-sided 5% significance level. No adjustments for multiplicity will be made for secondary and exploratory endpoints.

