6 EFFICACY ANALYSES

6.1 Analysis of the Primary Efficacy Endpoint

Analysis of the primary efficacy endpoints will be performed on the modified ITT data set, first on the entire cohort, then within the subgroups of patients with and without diabetes, and then within other subgroups as specified in section 2.3. Sensitivity analyses will be performed as outlined in section 2.3; in addition, supportive analyses will be repeated using the same models on the on-treatment set (OTS) and per-protocol set (PPS), as applicable.

Mean, standard deviation, median, and interquartile range (IQR) will be reported for KCCQ clinical summary score and for its change at 12-week follow-up, for the entire cohort and by treatment group.

An ACCOVA model will be used to estimate the effect of dapagliflozin on the 12-week KCCQ clinical summary score, adjusting for baseline KCCQ clinical summary score, sex, eGFR, Diabetes status, permanent atrial fibrillation status, and LVEF. Patient participation in the Echocardiography sub-study will not be controlled for because we don't hypothesize that participation in the Echocardiography sub-study is associated with the primary outcome (KCCQ CS).

A sensitivity analysis will repeat the primary analysis but will also include site as a random effect to account for potential clustering by enrolling center. Another sensitivity analysis will be performed using the imputed KCCQ values as described in section 2.6.

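### The protocol sizes the diabetes strata to look for effect modification, but the SAP names no treatment-by-diabetes contrast, and separate within-stratum p-values cannot answer that question

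*SAP*

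**What the plan says.** - **Purpose.** Protocol 12.2 (repeated in the synopsis) gives each diabetes stratum its own sample size and power. It says the numbers are enough "to examine whether important interactions exist in the effects of dapagliflozin vs. placebo by diabetes status". The only method it gives is to repeat the primary analysis inside each stratum. Diabetes status is also a randomisation stratum.
- **SAP 2.3, diabetes.** "All efficacy and safety endpoints will be analyzed in the entire cohort, and then within the subgroups of patients with and without diabetes".
- **SAP 2.3, other variables.** The section then turns, with the word *Additionally*, to a list for the primary endpoint: NTproBNP, LVEF, AF type, KCCQ overall summary score, eGFR, age, sex, race, BMI, loop diuretic dose and NYHA class. After the list it says that subgroup analyses add the subgroup and its interaction with treatment to the primary model, and report an interaction p-value. Diabetes is not among the eleven variables.
- **SAP 6.1.** The primary analysis is run on the entire cohort, "then within the subgroups of patients with and without diabetes, and then within other subgroups as specified in section 2.3".
- **SAP 2.5.** "The primary endpoint will be tested at the 2-sided 5% significance level". Secondary and exploratory endpoints carry no multiplicity adjustment.

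**The concern.** Whether the effect differs by diabetes status is a question about the difference between two treatment effects. Two separate tests, one per stratum, do not estimate that difference. Each asks only whether the effect in its own stratum can be told from zero, and the answer depends on stratum size as well as on the drug. When the strata are of unequal size and each is modestly powered for the overall design effect, one significant and one non-significant result is a common outcome under a uniform effect.

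As written, the plan names an interaction test for age, race and BMI but not for the one baseline factor that the protocol singles out for interactions. At stake is a report that the drug works in one diabetes group and not in the other, with no prespecified contrast to set against it.

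**Working it through.** **Inputs**
- Two-sided alpha 0.05 (SAP 2.5).
- Effect and SD (SAP 1.3): "the adjusted mean difference between dapagliflozin group and placebo group is 4.7 and the standard deviation is 13.7".
- Equal allocation (SAP 1.3): "Approximately 160 patients will be enrolled in each arm".
- Evaluable patients per arm (Protocol 12.2): 87 without diabetes and 58 with diabetes, which sum to 145.

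**Step 1: reproduce the plan's own power figures**

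SE = SD × √(2/n), and power ≈ Φ(difference/SE − 1.96).

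| Group | n per arm | SE | Difference | Power | Plan states |
|---|---|---|---|---|---|
| Whole cohort | 145 | 13.7 × √(2/145) = 1.609 | 4.7 | Φ(2.921 − 1.96) = 83.2% | 82% |
| No diabetes | 87 | 13.7 × √(2/87) = 2.077 | 5.9 | Φ(2.840 − 1.96) = 81.1% | 80% |
| Diabetes | 58 | 13.7 × √(2/58) = 2.544 | 7.2 | Φ(2.830 − 1.96) = 80.8% | 80% |

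Noncentral-t values are 82.9%, 80.6% and 80.1%. The whole-cohort figure matches the SAP statement: "For the primary endpoint a sample size of 145 for each group will achieve 82% power". All three agree with the plan, so the inputs are the sponsor's own.

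**Step 2: power in each stratum if the effect is 4.7 in both**
- No diabetes: Φ(4.7/2.077 − 1.96) = 61.9% (noncentral t 61.4%).
- Diabetes: Φ(4.7/2.544 − 1.96) = 45.5% (noncentral t 44.9%).

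**Step 3: chance that the strata disagree**

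The strata contain different patients, so the two tests are treated as independent.
- Significant without diabetes only: 0.619 × (1 − 0.455) = 33.7%.
- Significant with diabetes only: 0.455 × (1 − 0.619) = 17.3%.
- Exactly one significant: 51.1% (noncentral t 51.2%).
- Both significant: 28.2%. Neither: 20.8%.

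**Step 4: how far this depends on the assumptions**

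| Common effect (SD 13.7) | 2 | 3 | 4 | 4.7 | 5.9 | 7.2 |
|---|---|---|---|---|---|---|
| Exactly one significant | 24% | 39% | 49% | 51% | 42% | 24% |

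With the effect held at 4.7:
- If diabetes reaches the 45% cap in Protocol 4 (80 and 65 per arm), the figure is 50%.
- With no dropout (96 and 64 per arm) it is 50%.
- At assumed SDs of 12, 16 and 20 it is 48%, 50% and 42%.
- Among trials with a significant whole-cohort result it is about 57% (simulation, normal approximation).

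**Step 5: what a direct contrast would show**
- SE of the between-stratum difference = √(2.077² + 2.544²) = 3.28 points, so the 95% CI half-width is 1.96 × 3.28 = 6.4 points.
- Under a common effect, the interaction test is significant in 5% of trials by construction. Among discordant trials the simulation gives about 9%, so in about 91% of them the contrast would show no evidence of heterogeneity.
- Power for a true between-stratum difference of 4.7 is Φ(4.7/3.28 − 1.96) ≈ 30%.
- The difference detectable with 80% power is (1.96 + 0.84) × 3.28 ≈ 9.2 points.

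**The case against.** **The SAP may already cover diabetes.** SAP 2.3 itself calls the diabetes groups subgroups, SAP 6.1 speaks of *other* subgroups after them, and the sentence on adding an interaction term is general. Diabetes is already a covariate in the primary model, so the term would fit directly. This stands in part. A reader might infer that the plan rules out any test by diabetes, and the documents do not go that far. But *Additionally*, the explicit list and the two-step order in 6.1 point away from diabetes being included, and no sentence names the contrast.

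**The 51% is conditional and generic.** This stands. It holds near the design effect and falls on either side of it, and any trial split into modestly powered strata behaves this way. It shows why separate p-values cannot answer the protocol's question. The missing list entry does not cause the discordance.

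**An interaction test would not repair discordant results.** This also stands. A reader might infer that adding the test corrects them. It only guards against misreading them, and with little power.

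**No misreading is planned.** True: nowhere do the documents say that stratum p-values will be compared, and Protocol 12.2 calls the no-diabetes results preliminary. But the protocol does say that interactions will be examined and gives no other method.

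**Permanent AF.** A reader might extend the point to this stratum, because the SAP list pools permanent with persistent AF: "Atrial fibrillation type (No AFib, permanent/persistent AFib, paroxysmal AFib". The documents do not support that. They promise no interaction by permanent AF, an AF-type interaction is already planned, and being a stratification factor does not oblige a test.

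**Conclusion.** The concern holds as a mismatch between stated purpose and specified method. The protocol wants to know whether the effect differs by diabetes status. The SAP specifies two separate analyses for diabetes and, at best by inference, a contrast. With a common effect of 4.7, SD 13.7 and 87 and 58 patients per arm, exactly one stratum is significant in about 51% of trials. Across common effects of 2 to 7.2 points the figure runs from 24% to 51%.

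These figures assume the same SD in both strata, the planned 60:40 split, and the planning SD as the residual SD; the documents do not say whether 13.7 is raw or covariate-adjusted.

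The whole-cohort primary test and its type I error are unaffected, so this is a correction worth making before unblinding and no threat to the main result. A non-significant interaction would not show that the effects are equal, since only differences near 9 points could be detected reliably.

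**What to change.** In SAP 2.3:
1. Add diabetes (yes, no) to the list of subgroup variables that receive the interaction model for the primary endpoint.
2. From that augmented primary model, report the between-stratum difference in treatment effect with its 95% CI and the interaction p-value. Keep the planned within-stratum analyses alongside; they need not be replaced.
3. State that a significant result in one stratum and not in the other is not evidence of a differential effect.
4. Acknowledge the precision: about 30% power for a 4.7-point difference between strata, and 80% only near 9.2 points.

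The cost is a few lines of SAP text and one extra model term. It needs no new data, no change in sample size and no change to the primary test.

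### SAP 2.3 tests effect modification by measured baseline variables only on two-way splits; if a modifier is roughly normal and acts linearly, a median split loses about 36% of the information on the interaction

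*SAP*

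**What the plan says.** SAP 2.3 lists the subgroup factors for the primary endpoint. Seven are measured quantities reduced to two groups:

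- **Cut at the sample median:** NT-proBNP, BMI and KCCQ overall summary score, the last written as "Baseline KCCQ overall summary score (<median" against the rest.
- **Cut at one fixed point:** LVEF (60%), eGFR (60 mL/min/1.73 m²), age (70) and furosemide-equivalent mean daily dose (40 mg).

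The method is: "Subgroup analyses will be carried out by augmenting the primary analysis model with terms for subgroup and a subgroup-by-treatment interaction". The output is an adjusted estimate with a 95% interval in each subgroup, and an interaction p-value. SAP 6.1 only refers back to 2.3.

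The same section allows flexible modelling of measured values: "Restricted cubic splines will be used for continuous variables to accommodate non-linear effects, as appropriate". That sentence follows the list of adjustment covariates and is not linked to treatment. Neither the SAP nor the Protocol plans an interaction between treatment and a continuous baseline value.

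**The concern.** A two-level term treats a patient just above the cut like one far above it. If the treatment effect changes gradually with the baseline value, that discards information the trial has already collected. For eGFR and LVEF the measured value is already a covariate in the primary ANCOVA, so the interaction ignores information the same model holds. The median cuts also depend on the sample and have no fixed boundary until the data are in.

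At stake is how the subgroup p-values are read. Interaction tests at this sample size are already weak. Weakening them further makes a real gradient easier to miss, and a non-significant p-value easier to take as evidence that the effect is uniform.

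**Working it through.** **Inputs.** SAP 2.5 gives alpha: "The primary endpoint will be tested at the 2-sided 5% significance level". SAP 1.3 gives the size, "For the primary endpoint a sample size of 145 for each group will achieve 82% power", and the assumptions, "adjusted mean difference between dapagliflozin group and placebo group is 4.7 and the standard deviation is 13.7". Allocation is equal: "Approximately 160 patients will be enrolled in each arm".

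**The plan's own figure.** The SE of the difference is 13.7 × √(2/145) = 1.609, and 4.7/1.609 = 2.92. Power = Φ(2.92 − 1.96) = 83.2% (82.9% with the noncentral t), close to the stated 82%. For dropout, 290/0.9 gives 323 after rounding up, and 290 × 1.1 = 319. Both agree with about 320. The documents state no power for any interaction in this list.

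**Information kept by a split.** For an interaction linear in X, the share kept is the squared correlation between X and its two-level version. For normal X with a share q below the cut:

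kept = φ(z_q)² / [q(1 − q)]

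| Split | Kept | Lost |
|---|---|---|
| 50/50 | 0.637 (= 2/π) | 36% |
| 60/40 | 0.622 | 38% |
| 70/30 | 0.576 | 42% |
| 80/20 | 0.490 | 51% |
| 90/10 | 0.342 | 66% |

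The documents do not say what share of patients falls on each side of the four fixed cuts, so these rows are a range and not an estimate.

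**Other shapes.**
- A uniform modifier split at its median keeps 0.75 and loses 25%.
- A lognormal marker whose effect is linear on the raw scale (log-SD assumed 0.5 to 1.2) loses 48% to 82% at the median. If the effect is linear on the log scale, the loss is again 36%.
- A true step exactly at the cut loses nothing.

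**Power with n = 290 and SD 13.7.**
- SE of the interaction slope per SD of the modifier: 2 × 13.7/√290 = 1.609.
- Slope needed for 80% power on the continuous scale: (1.96 + 0.842) × 1.609 = 4.5 KCCQ points per SD.
- The same interaction after a median split: Φ(2.80 × √0.637 − 1.96) = Φ(0.275) = 61%.
- Equivalent sample: 290 × 0.637 ≈ 185 patients. To regain 80%: 290/0.637 ≈ 456.
- A simulation of 4,000 trials gave 78% (continuous) and 61% (split).

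**A smaller interaction.** Assume a slope of half the planned effect, 2.35 points per SD. Then 2.35/1.609 = 1.46. Power is Φ(1.46 − 1.96) = 31% on the continuous scale and Φ(1.46 × 0.798 − 1.96) = 21% after a median split.

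**A step effect.** When the true modifier was a step at the population median, the simulation gave 76% power for the split and 60% for the linear term.

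**The case against.** The plan contains no error here. The factors are pre-specified, the interaction is tested formally inside the adjusted primary model, and estimates with intervals are reported. No decision rule hangs on these p-values. The subgroup that the Protocol sizes for is diabetes status (Protocol 12.2), which is a category by nature. All of this stands, and it is why the point is an improvement and not a defect.

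The 80%-to-61% example also needs a very large interaction. A slope of 4.5 points per SD is nearly the whole planned effect of 4.7, so benefit would run from about 0 at one SD below the mean to about 9 at one SD above. For smaller slopes both tests usually miss. This stands too and limits the practical gain.

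A linear term is an assumption in its own right, and under a step effect the split is the stronger test. A threshold is not an arbitrary question for eGFR, since Protocol 1.3.2 discusses a labelling limit at 60. A reader might infer that the continuous p-value should replace the split one. The documents do not support that, because nothing in them says which shape is true. The objection therefore rules out replacement, but it does not count against adding a test.

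**Conclusion.** The point holds as a cheap improvement. For the three median splits the loss is about 36%, provided that the modifier is roughly normal (NT-proBNP on the log scale) and its effect is linear. Under the same assumptions 36% is the smallest loss for the fixed cuts, rising to about 51% at 80/20. Other shapes range from no loss (a step at the cut) through 25% (uniform) to well over half (a skewed marker acting on the raw scale).

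Three stronger readings are tempting, and the documents do not support them:

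- **That every interaction p-value loses about a third.** The documents give no distribution for any of these variables and no shares around the fixed cuts.
- **That the primary model already holds all the discarded information.** This is true of eGFR and LVEF only. NT-proBNP, BMI, age and diuretic dose are not primary covariates, and the KCCQ covariate is the clinical summary score, whereas the subgroup uses the overall summary score.
- **That the plan will declare the effect consistent across subgroups.** Neither document plans that conclusion.

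The primary test and its power are untouched.

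**What to change.** In SAP 2.3, keep every listed cut-point with its subgroup estimates, confidence intervals and interaction p-value. Add, before unblinding, one treatment-by-continuous-baseline interaction test for each of log NT-proBNP, KCCQ overall summary score, BMI, LVEF, eGFR and age, fitted in the primary ANCOVA. Where the measured value is not already a covariate, its main effect enters as well. Say that both p-values will be reported for each variable whatever they show, so that neither can be chosen afterwards.

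Consider the same for furosemide-equivalent dose. SAP 4.3 sets the dose to zero for patients not on a loop diuretic, so a normal, linear description may suit it less well.

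The cost is a few lines of SAP text and six model terms (seven with diuretic dose), using baseline data already planned for collection. The downside is six or seven more exploratory p-values. A linear term can also miss a threshold effect, which the retained split test covers.
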